9.4.5.4. Magnetic Resonance Imaging

Magnetic resonance imaging of the brain will be performed according to the Schedule of Activities (Section 2) to screen patients for eligibility to participate in the study and for secondary efficacy assessment. Magnetic resonance imaging screening scans should be performed during the screening period, after the patient has met most other screening criteria, as outlined in the Schedule of Activities (Section 2). The central radiologist review of the screening MRI scan must be available before randomization to evaluate the inclusion/exclusion criteria. Any clinically significant findings that result in a diagnosis should be recorded as a pre-existing condition or AE per Section 9.2.

Magnetic resonance imaging scanning will be conducted under the management of a central vendor. The scans will be reviewed by the investigator or qualified designee for immediate patient management. The MRI scans will be acquired at the imaging sites using a standardized protocol. The MRI scans will be transmitted to the imaging vendor for evaluation.

If a patient develops an acute neurological change such as symptoms suggestive of vasogenic edema during the study, an unscheduled MRI should be obtained. Potential symptoms of ARIA-E could include headache, gait instability, dizziness, tremor, worsening cognitive function, alteration of consciousness, seizures, unsteadiness, and vomiting (Ostrowitzki et al. 2012; Sperling et al. 2012). The abnormality is best detected by fluid attenuation inversion recovery

(FLAIR) sequences on the MRI and ARIA-H is detected with the T2* gradient-recalled echo on the MRI. It is recommended to repeat the MRIs with these sequences every 2 to 4 weeks until resolution of ARIA-E is documented. For asymptomatic or mild symptoms, the patient can be observed; for moderate symptoms, the use of oral or IV steroids can be considered. In the case of severe symptoms, it is recommended to hospitalize the patient for close observation and consider the use of IV steroids such as high-dose dexamethasone or a similar agent. Study treatment should be discontinued if clinically symptomatic vasogenic edema, clinical symptomatic superficial siderosis, or clinically symptomatic incident microhemorrhage is seen.

Magnetic resonance imaging findings believed to have potential clinical significance will be reported to the investigator and sponsor. Any new or aggravated clinically relevant abnormal MRI finding as compared with the baseline MRI should be reported to Lilly or its designee as an AE via an eCRF per Section 9.2. If a clinically meaningful change in MRI is noted during the study, an additional, full neurological exam will be performed as soon as possible, along with any other medical follow-up deemed necessary by the investigator (Section 9.4.4).

9.4.6. Safety Monitoring

Lilly will periodically review evolving aggregate safety data within the study by appropriate methods. An AC will be designated for at least one interim evaluation of unblinded safety data from Study LLCF (Section 10.3.7).

If a study patient experiences elevated ALT \geq 3X ULN, ALP \geq 2X ULN, or elevated TBL \geq 2X ULN, hepatic laboratory tests (Appendix 4) must be repeated within 3 to 5 days including ALT, AST, ALP, TBL, direct bilirubin, gamma-glutamyl transferase, and creatine kinase to confirm the abnormality and to determine if it is improving or worsening. If the abnormality persists or worsens, clinical and laboratory monitoring must be initiated by the investigator and in consultation with the study medical monitor. Monitoring of ALT, AST, TBL, and ALP must continue until levels normalize or return to approximate baseline levels.

Additional safety data must be collected via the case report form (CRF) if 1 or more of the following conditions occur:

- Elevation of serum ALT to ≥5X ULN on 2 or more consecutive blood tests
- Elevated serum TBL to ≥2X ULN (except for cases of known Gilbert's syndrome)
- Elevation of serum ALP to >2X ULN on 2 or more consecutive blood tests
- Patient discontinued from treatment due to a hepatic event or abnormality of liver tests
- Hepatic event considered to be a SAE

See Appendix 4, for hepatic eCRFs that must be completed for these patients.

9.5. Pharmacokinetics

At the visits and times specified in the Schedule of Activities (Section 2), venous blood samples of approximately 3 mL each will be collected to determine the plasma concentrations of LY3202626

A maximum of 2 samples may be drawn at additional time points during the study if warranted and agreed upon between both the investigator and sponsor. Instructions for the collection and handling of blood samples will be provided by the sponsor. The actual date and time (24-hour clock time) of each sampling will be recorded.

Drug concentration information that may unblind the study will not be reported to investigative sites or blinded personnel until the study has been unblinded.

Bioanalytical samples collected to measure LY3202626 concentrations will be retained for a maximum of 1 year following last subject visit for the study. During this time, samples remaining after the bioanalyses may be used for exploratory analyses such as metabolism and/or protein binding work.

9.6. Pharmacodynamics

The peripheral dose-dependent PD activity of LY3202626 and placebo administration will be evaluated by analysis of plasma $A\beta_{1-40}$, $A\beta_{1-42}$, $A\beta_{1-x}$ as measured using validated immunoassays. These plasma based biomarkers will provide an assessment of target engagement and the data will inform dose optimization. Central PD will be assessed in a substudy in which CSF is collected from participating patients.

Biological samples collected to measure PD parameters will be identified by the patient number (coded) and retained for a maximum of 15 years following last patient visit for the study at a facility selected by Lilly or its designee.

9.7. Genetics

9.7.1. Apolipoprotein E Genotyping

Apolipoprotein E (APOE) genotyping is a mandatory part of this study, unless country-specific laws and regulations prohibit this type of testing. Blood sampling for APOE genotyping will be performed as shown in the in the Schedule of Activities (Section 2). Neither patients nor investigators will receive the genotype results unless there is a country-specific law or regulation that requires notification of the results. Failure to collect samples for APOE will not be considered a protocol deviation if country-specific regulations prohibit the testing of genetic material or transportation of such material outside of the country.

9.7.2. Whole Blood Sample for Pharmacogenetic Research

A whole blood sample will be collected for pharmacogenetic analysis as specified in the Schedule of Activities (Section 2) where local regulations allow.

Samples will not be used to conduct unspecified disease or population genetic research either now or in the future. Samples will be used to investigate variable response to LY3202626 and to investigate genetic variants thought to play a role in AD. Assessment of variable response may include evaluation of AEs or differences in efficacy.

All samples will be coded with the patient number. These samples and any data generated can be linked back to the patient only by the investigator site personnel.

Samples will be retained for a maximum of 15 years after the last patient visit for the study, or for a shorter period if local regulations and/or ethical review boards (ERBs)/investigational review boards (IRBs) impose shorter time limits, at a facility selected by Lilly. This retention period enables use of new technologies, response to regulatory questions, and investigation of variable response that may not be observed until later in the development of LY3202626 or after LY3202626 become(s) commercially available.

Molecular technologies are expected to improve during the 15-year storage period and therefore cannot be specifically named. However, existing approaches include whole genome, exome or directed next-generation sequencing, genome wide association studies, and candidate gene studies. Regardless of technology utilized genotyping data generated will be used only for the specific research scope described in this section.

9.8. Biomarkers Research & Development

Biomarker research is performed to address questions of relevance to drug disposition, target engagement, PD, mechanism of action, variability of patient response (including safety), and clinical outcome. Sample collection is incorporated into clinical studies to enable examination of these questions through measurement of biomolecules including deoxyribonucleic acid (DNA), ribonucleic acid (RNA), proteins, lipids, and other cellular elements.

Plasma and whole blood samples for RNA and epigenetic analyses will be collected for non-pharmacogenetic biomarker research at the times specified in the Schedule of Activities (Section 2) where local regulations allow.

Samples will be used for research on the drug target, disease process, variable response to LY3202626, pathways associated with AD, mechanism of action of LY3202626, and/or research methods or in validating diagnostic tools or assay(s) related to AD.

All samples will be coded with the patient number. These samples and any data generated can be linked back to the patient only by the investigator site personnel.

Samples will be retained for a maximum 15 years after the last patient visit for the study, or for a shorter period if local regulations and ERBs impose shorter time limits, at a facility selected by Lilly or its designee. This retention period enables use of new technologies, response to regulatory questions, and investigation of variable response that may not be observed until later in the development of LY3202626 or after LY3202626 becomes commercially available.

9.9. Medical Resource Utilization and Health Economics

Health Economics and Medical Resource Utilization parameters were not evaluated in this study.

10. Statistical Considerations

10.1. Sample Size

Approximately 380 patients will be enrolled so that approximately 320 patients will complete the study.

Patients who are randomized but not administered treatment may be replaced to ensure that enough subjects complete the study.

10.1.1. Sample size calculation

The sample size was determined based on internal, 9-month, longitudinal ¹⁸F-AV-1451 data. ¹⁸F-AV-1451 SUVr values were calculated from these images using the CC as the reference region (CC) the CC . The map providing the CCI (MUBADA) (Abdi 2012) and corresponds to an intensity map that reflects the cross-sectional difference in ¹⁸F-AV-1451 signal between AD subjects and healthy controls. This map is most ;CCI Approximately 380 patients will be randomized into the trial according to a treatment ratio 1:1:1 for LY3202626 3 mg, LY3202626 12 mg, and placebo, until approximately 45 participants are enrolled into each arm, then 1:1 in the LY3202626 12 mg and placebo arms until 380 total have been randomized. A sensitivity analysis was performed on drop-out rates as high as 30%, and the power for the

primary outcome was no worse than 79%.

```
With respect to CC
                                                                             Based on
research by Schott and colleagues (2010), CC
                                CCI
```

10.2. Populations for Analyses

Analysis populations for Study LLCF are defined below (Table LLCF.3).

Table LLCF.3. Analysis Populations

Population	Description	
Enrolled	All participants who have been assigned to treatment (randomized).	
Efficacy	All randomized participants who take at least 1 dose of double-blind study	
	treatment and have at least 1 postdose efficacy measurement.	
Safety All randomized participants who take at least 1 dose of double-blind stu		
	treatment.	

Note: Participants will be included in the treatment group to which they were randomized.

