10.3. Statistical Analyses

10.3.1. General Statistical Considerations

Statistical analysis of this study will be the responsibility of Eli Lilly and Company.

Unless otherwise specified, all safety analyses will be conducted on the safety population and all efficacy and PD analyses will be conducted on the efficacy population as defined above (Table LLCF.3).

No adjustments will be made for multiple comparisons.

All total and subscale scores will be derived from individual items. If any individual item is missing, the corresponding total and subscale scores will be considered missing, except for the ADAS-Cog₁₃, which will be imputed. The imputation algorithm will be specified in the statistical analysis plan (SAP).

All tests of treatment effects of biological efficacy or clinical efficacy will be conducted at a 1-sided α =.10, unless otherwise stated. Safety assessments will be conducted at a 2-sided α =.05.

A repeated measures analysis refers to a restricted maximum likelihood (REML)-based, mixed effects repeated measures analysis using all the longitudinal observations at each post-baseline

visit. A repeated measures analysis model will include the fixed, categorical effects of treatment group, visit, and treatment-by-visit interaction, as well as the continuous, fixed covariates of baseline and the baseline-by-visit interaction, unless otherwise noted. Unless otherwise specified, when an ANOVA model is used to analyze a continuous efficacy variable, the model will contain the main effects of treatment. Similar logic is applied to an ANCOVA model, which in general, refers to the ANOVA model with baseline value added as a covariate. Type III sum-of-squares for the least squares (LS) LS Means will be used for statistical comparisons using an ANOVA or ANCOVA. Categorical comparisons between treatment groups will be performed using Fisher's exact tests, where appropriate.

Any change to the data analysis methods described in the protocol will require an amendment to the protocol only if it changes a principal feature of the protocol. Any other change to the data analysis methods described in the protocol, and the justification for making the change, will be described in the clinical study report (CSR). Additional exploratory analyses of the data will be conducted as deemed appropriate.

SAS® software will be used to perform most or all statistical analyses.

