## 5. A Priori Statistical Methods

### 5.1. General Considerations

All tests of treatment effects of biological efficacy or clinical efficacy will be conducted at a 1-sided  $\alpha=.10$ , unless otherwise stated. Safety assessments will be conducted at a 2-sided  $\alpha=.05$ .

A repeated measures analysis refers to a restricted maximum likelihood (REML)-based, mixed effects repeated measures analysis using all the longitudinal observations at each post-baseline visit.

All analyses will follow the intent-to-treat (ITT) principle unless otherwise specified. An ITT analysis is an analysis of data by the groups to which subjects are assigned by random allocation, even if the subject does not take the assigned treatment, does not receive the correct treatment, or otherwise does not follow the protocol.

When change from baseline is assessed, subjects will be included in the analysis only if both a baseline and a postbaseline measure are available. Unless otherwise defined, Visit 3 is the baseline visit, and baseline value is defined as last value available before or at Visit 3.

All total and subscale scores will be derived from individual items. If any individual item is missing, the corresponding total and subscale scores will be considered missing, except for the ADAS-Cog13 and ADCS-iADL, which will be imputed.

A repeated measures analysis model will include the fixed, categorical effects of treatment, visit, and treatment-by-visit interaction, as well as the continuous, fixed covariates of baseline, baseline-by-visit interaction, and age at baseline.

When an analysis of covariance (ANCOVA) model is used to analyze a continuous efficacy variable, the model will contain the main effects of treatment with baseline value and age at baseline added as covariates. For ANCOVA analysis on change from baseline to Week 52 endpoint, change from baseline to last observation during treatment period will be used if patients do not have Week 52 observation available.

Categorical comparisons between treatment groups will be performed using Fisher's exact tests or logistic regression where appropriate.

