### **5.6. Population for Analysis**

The Efficacy population is defined as all randomized participants who take at least 1 dose of double-blind study treatment and have at least 1 postdose efficacy measurement, which is used to assess the effectiveness of the study drug regimen; all observed data will be included (including data gathered after a subject discontinues study drug).

In order to assess the study drug treatment effect, data gathered after a subject discontinues study drug will not be included in the analysis of per protocol population.

Additionally, when change from baseline is assessed, subjects will be included in the analysis only if both a baseline and at least 1 valid post-baseline measure are available.

All subjects who received at least 1 dose of randomized study treatment (LY3202626 or placebo) will be included in the safety analysis set. If an LY3202626 dose group is dropped following an interim analysis, subjects switched to the remaining LY3202626 dose and remaining on treatment will be accounted for as a separate group.

For the Lumbar Puncture addendum, the analysis sets will include all those subjects whose eligibility was determined by the respective biomarker, who signed consent for addendum, and who have a baseline and at least 1 valid post-baseline cerebrospinal fluid (CSF) assessment.

The PK analysis set is defined as all subjects in the safety population who have at least 1 post-dose PK assessment. The population PK analyses will be performed using this analysis set.

The primary and secondary efficacy measures will be analyzed using the efficacy population unless otherwise specified. In addition, the primary measure will be analyzed using per-protocol populations to verify the robustness of the results. Summaries and analyses for safety measures will be based on the safety population.

[Table LLCF.SAP.1](#) below defines each of the analysis populations used in this study.

[Table LLCF.SAP.2](#) lists the study measures that will be summarized and/or analyzed for each population.

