**Table LLCF.SAP.1. Analysis Populations for Study I7X-MC-LLCF**

Population Name	Description of Population
Enrolled	All participants who have been assigned to treatment (randomized).
Efficacy	All randomized participants who take at least 1 dose of double-blind study treatment and have at least 1 postdose efficacy measurement.
Safety	All randomized participants who take at least 1 dose of double-blind study treatment.
Per-Protocol	All subjects in the Full Efficacy population who also: 
 
• had an assessment of the primary endpoint at each scheduled visit completed
 
• had no violations of inclusion/exclusion criteria
 
• had no study dosing algorithm violation (such as if subjects randomized to treatment A were given treatment B or subjects randomized to treatment A never received the assigned study drug)
 
• had no unqualified raters and no raters with substantial scoring errors for the primary measure
 
• was not considered non-compliant with regard to study drug
 

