#### **5.14. Safety Follow-up Visit**

Follow-up visit (Week 56) is not required for patients who discontinue study treatment early and who continue in the study unless study drug was discontinued within the last 4 weeks of the study.

Adverse events, concomitant medications, vital signs, and ECGs will be collected at these visits. These data will be summarized by treatment received during placebo-controlled treatment period.

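### Treatment-period safety data follow the randomized arm even after wrong-treatment dosing, while follow-up safety data, read literally, follow treatment received; one rule by treatment received should cover both

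*Protocol*

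**What the plan says.** Protocol 10.2, Table LLCF.3, defines the Enrolled, Efficacy and Safety populations and closes with one unqualified note: "Participants will be included in the treatment group to which they were randomized". Protocol 10.3.1 adds that, unless otherwise specified, "all safety analyses will be conducted on the safety population".

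SAP 5.1 sets the default: "All analyses will follow the intent-to-treat (ITT) principle unless otherwise specified". It defines this as analysis by assigned group, "even if the subject does not take the assigned treatment, does not receive the correct treatment, or otherwise does not follow the protocol".

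SAP 5.6 settles who is in the safety set: "All subjects who received at least 1 dose of randomized study treatment (LY3202626 or placebo) will be included in the safety analysis set". Neither that section nor Table LLCF.SAP.1 says that safety data are grouped by treatment received. SAP 5.6 has one departure from the randomized arm: if a dose is dropped at an interim analysis, "subjects switched to the remaining LY3202626 dose and remaining on treatment will be accounted for as a separate group".

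SAP 5.14 lists adverse events, concomitant medications, vital signs and ECGs at follow-up, and then states: "These data will be summarized by treatment received during placebo-controlled treatment period".

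The SAP foresees wrong-treatment dosing. The Per-Protocol definition in Table LLCF.SAP.1 gives as an example of a dosing violation that "subjects randomized to treatment A were given treatment B". SAP 5.15 repeats the example in its violation listing, which covers the efficacy population.

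**The concern.** Keeping patients in their randomized arm protects the efficacy comparison. In safety tables it works the other way when someone has taken the wrong product, because events are counted against a treatment the patient was not taking. Each kind of error has its own effect:

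- A placebo-assigned patient who took LY3202626 adds drug events to placebo.
- A drug-assigned patient who was given placebo adds unexposed time to the drug arm and dilutes its rate.
- A mix-up between 3 mg and 12 mg leaves the placebo arm intact but blurs the dose comparison.

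The first two pull a true excess of harm toward no difference, which is the unfavourable direction for safety. Safety and tolerability are secondary objectives, and Protocol 3.2 makes them the main focus of the 3 mg arm. The events of special interest in Table LLCF.SAP.3 include retinal, pigmentation, hepatic and arrhythmic groups, any of which could rest on a few patients.

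There is also an inconsistency. Under the literal wording, the same misdosed patient could sit in placebo in the SAP 5.13 tables and in LY3202626 in the follow-up summary.

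**Working it through.** **Attribution rule, place by place**

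| Place | Data | Group used |
|---|---|---|
| Protocol Table LLCF.3 note | All three populations | Randomized |
| SAP 5.1 | All analyses unless otherwise specified | Randomized, wrong treatment included |
| SAP 5.6 | Safety set, patients switched after a dose is dropped | Separate group |
| SAP 5.13 | Treatment-period safety | No rule of its own, so the SAP 5.1 default applies |
| SAP 5.14 | Follow-up AEs, concomitant medications, vital signs, ECGs | Treatment received |

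**Planned size.** Protocol 5.1 gives about 167 + 167 + 45 = 379, against the stated approximate 380. The allocation rule agrees: 45 + (380 − 135)/2 = 167.5 per large arm. The documents give no misdosing count, event rate or safety power, so those values below are assumptions.

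**Average effect.** Let n = 167 per arm, let p1 and p0 be the event risks on drug and placebo, and let m placebo-assigned patients take drug.

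- As-randomized placebo risk = [(n − m)·p0 + m·p1]/n
- As-randomized difference = (p1 − p0)·(1 − m/n)
- Shrinkage per patient = 1/167 = 0.6% of the difference

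Power is for Fisher's exact test, 2-sided 0.05, 167 v 167:

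| m | Difference, 10% v 2% | Power, 10% v 2% | Power, 5% v 0% |
|---|---|---|---|
| 0 | 8.0 points | 85.4% | 84.6% |
| 1 | 8.0 × 166/167 = 7.95 | 84.7% | 83.3% |
| 5 | 8.0 × 162/167 = 7.76 | 81.8% | 78.3% |
| 17 | 8.0 × 150/167 = 7.19 | 72.0% | 63.6% |

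One to five such patients therefore cost about 1 to 6 points of power. If errors go both ways in equal number, the factor becomes (1 − 2m/n): for m = 1 the difference is 7.90 points and power is 84.3%.

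**Rare event, adverse case.** Suppose one placebo-assigned patient takes drug and is also one of the patients with the event. Fisher's exact p, 2-sided:

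| Comparison | By treatment received | As randomized |
|---|---|---|
| 12 mg v placebo | 6/168 v 0/166, p = 0.030 | 5/167 v 1/167, p = 0.21 |
| 3 mg v placebo | 2/46 v 0/166, p = 0.046 | 1/45 v 1/167, p = 0.38 |

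These are chosen cases. If the risk on drug is 6/168 = 3.6%, a given misdosed patient has only about that chance of being an event case.

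**The case against.** The strongest reply is that this is hypothetical. No misdosing rate is given. Protocol 7.2 has bottles assigned by the web-response system, and sites must enter a confirmation number from the container, which guards against wrong dispensing. The average loss from one error is about 1 power point or less under the assumed rates. The 167 per arm is the plan, and the SAP revision history records early termination, so the analysed numbers may differ. All of this stands and limits the size of the point.

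The conflict between the SAP sections can also be read more gently. SAP 5.1 allows exceptions, so SAP 5.14 could be one. Its wording may also mean no more than the group a patient belonged to before follow-up. That is plausible, but the text does not say so, and the protocol note carries no such qualifier. The Schedule of Activities has no skin or eye examination at follow-up, so the two-rule conflict does not reach those examination data. Only the treatment-period attribution does.

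Misdosed patients are not invisible. SAP 5.15 lists dosing violations and SAP 5.13.2 lists adverse events, so a reader could put the two together. However, SAP 5.15 covers the efficacy population, so a patient with a dose but no post-dose efficacy measurement could be missed.

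A reader might infer that drug events will be charged to placebo and a safety signal hidden. The documents do not support that. It needs a placebo-assigned patient to receive drug, and nothing shows that this happened or was likely.

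**Conclusion.** The point holds in a limited form. The plan attributes treatment-period safety data to the randomized arm even after wrong-treatment dosing, and its follow-up wording, read literally, uses a different rule. If misdosing occurs, exposure is misattributed, in a direction that depends on the error.

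The expected effect is small: about 0.6% of the risk difference per misdosed placebo patient with 167 per arm, and zero without misdosing. It could matter for a rare event or in the 3 mg arm of about 45. The p-values above show how far one patient can move a sparse table and are not a forecast. They rest on assumed event counts, planned arm sizes and one misdosed patient who also has the event.

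This is a low-priority improvement that is worth making because it costs so little. It does not touch the primary PET analysis.

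**What to change.** - In Protocol Table LLCF.3, limit the as-randomized note to the Enrolled and Efficacy populations. State there and in Table LLCF.SAP.1 that the Safety population is analysed by treatment actually received, and name this in SAP 5.1 as an exception to intent-to-treat.
- Apply that rule in both SAP 5.13 and SAP 5.14, keeping the separate group for patients switched after a dose is dropped.
- Set one rule for mixed exposure in advance. One option is the treatment taken for most of the exposure period, with events during the other exposure flagged. Assigning patients to the highest dose ever taken is less suitable: one wrong bottle would move all of a placebo patient's events, including those before the error, to a drug arm.
- Extend the SAP 5.15 dosing-violation listing to the Safety population and show those patients' adverse events in it.

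The cost is a few lines of text and one actual-treatment variable. The downside is that misdosed patients leave their randomized group, for safety tables only.
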